## 4 Data Analysis

Data analysis will be performed by PPD. The statistical analysis software used will be SAS version 9.4 in a WINDOWS environment.

Prior to database closure a Blind Data Review Meeting (BDRM) will be conducted in which various aspects of the trial will be discussed and agreed.

### 4.1 Populations for Analysis

Tables described in this section will be produced for all randomized subjects.

### 4.1.1 Subject Disposition

Subject disposition will be summarized as the number and percentage of subjects who complete the study, with the number who discontinue broken down by reason for discontinuation (Table 14.1.1). Subject disposition including date of informed consent, date of first and last dose, completion status (Yes/No), completion or termination date and reason for discontinuation will be listed in Listing 16.2.1.1 by treatment group.

A listing of screen failures including date of screening and reason(s) for screen failure will be provided (Listing 16.2.1.2).

### 4.1.2 **Protocol Deviations**

All protocol deviations (both significant and non-significant) will be entered and tracked in PPD Clinical Trial Management System (CTMS) by the study team throughout the conduct of the study in accordance with PPD's Study Deviation Rules Document.

Significant protocol deviations that would exclude subjects from the Per Protocol (PP) population may include (but are not limited to) the following:

GlaxoSmithKline Consumer Healthcare Confidential

Page 10 of 22

- Major deviations in synovial tissue and synovial fluid sampling
- Subjects with poor compliance with study treatment
- Subjects taking prohibited medication or treatment during the study which is felt to affect the assessment of diclofenac concentration in synovial tissue and synovial fluid samples

Significant protocol deviations that would exclude subjects from the Per Protocol Pharmacodynamic (PP-PD) population may include (but are not limited to) the following:

- Major deviations in synovial tissue and synovial fluid sampling
- Subjects with poor compliance with study treatment
- Subjects taking NSAIDs or/and corticosteroids administered between screening and synovial samples collection
- Subjects taking other prohibited medications between screening and synovial samples collection which is felt to affect the assessment of pharmacodynamic biomarker

Data will be reviewed prior to closure of the database to ensure all significant deviations are captured and categorised.

Final list of significant protocol deviations leading to exclusion from the PP population (These were considered as major protocol deviations in protocol) and from the PP-PD population will also be determined by the study team.

The number and percentage of subjects with any significant protocol deviations and with each type of significant protocol deviations will be presented by treatment (Table 14.1.2) and listed in Listing 16.2.2.1. Any non-significant protocol deviations will be listed similarly (Listing 16.2.2.2).

Population	Definition / Criteria	Analyses Evaluated
Safety	
 
Comprised of all subjects who are randomized and have received at least one dose of investigational product.
 
	Safety
	
 
This population will be based on the treatment the subject actually received.
 
	
Analysable	• Comprised of all randomized subjects included in the safety population, who completed the surgery and have evaluable synovial tissue or synovial fluid sample.	
 
Primary, Secondary and Exploratory
 

	This population will be based on the treatment the subject actually received.	

### 4.1.3 Analysis Populations

Population	Definition / Criteria	Analyses Evaluated
Per Protocol (PP)	• Comprised of all randomized subjects from the analysable population who do not have any significant protocol deviations that could confound the interpretation of primary analyses conducted on the analysable population.	None
	
 
Protocol deviations that would exclude subjects from the PP population are defined in Section 4.1.2 (Protocol Deviations).
 
	
	• This population will be based on the treatment the subject actually received.	
Per Protocol Pharmacodynamic (PP-PD)	
 
Comprised of all randomized subjects from the analysable population who do not have any significant protocol deviations that could confound the interpretation of exploratory analyses for pharmacodynamic biomarkers (i.e. PGE2, IL-6 and TNFα).
 
	Exploratory
	
 
Protocol deviations that would exclude subjects from the PP-PD population are defined in Section 4.1.2 (Protocol Deviations).
 
	
	• This population will be based on the treatment the subject actually received.	

The numbers of subjects included in each of the analysis populations will be presented (Table 14.1.1). Subjects excluded from any of the analysis populations will be listed in Listing 16.2.3.1, with the reason for exclusion.

### 4.2 Subject Demographics and Other Baseline Characteristics

### 4.2.1 Demographic Characteristics

Categorical demographic variable includes sex. This variable will be summarized by the number and percentage of subjects with each relevant characteristic in each treatment group. Body Mass Index (BMI) will be calculated as weight (kg)/ [height (m)]. Age, weight, height and BMI will be summarized by the mean, standard deviation, median, minimum and maximum

GlaxoSmithKline Consumer Healthcare Confidential Page 12 of 22 values in each treatment group. All demographic information will be tabulated for the safety population (Table 14.1.3) and for the analysable population (Table 14.1.4). All demographic information will also be listed for safety population (Listing 16.2.4.1).

### 4.2.2 General Medical History

Medical history will be listed for the safety population by subject, with start date and end date or ongoing at the start of treatment with study drug (Listing 16.2.4.2).

# 4.3 Treatments (Study Drug, Rescue Medication, other Concomitant Therapies, Compliance)

Compliance data will be summarized for the analysable population. Exposure and other medications will be summarized on the safety population.

### 4.3.1 Study Drug Compliance

Study drug compliance is evaluated by the total number of applications and percentage of scheduled applications made. Percentage of scheduled applications made is defined as the number of applications made divided by the number of applications planned. The study drug will start to be applied on the day of randomization (Day 1) and continue to be applied twice daily until and including the day before surgery. The number of applications planned will be calculated as 2\*(date of last application-date of first application +1). Both compliance variables will be summarized descriptively for the analysable population. In addition, number and percentage of subjects with a minimum of 12 applications will be also presented (Table 14.2.1.1). Study drug accountability (Listing 16.2.5.1) and study drug administration (Listing 16.2.5.2) will also be listed for the safety population.

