#### 6.2.3 Pre-Surgery Day 7 and Surgery Day 8 (Visit 3)

The subject will be admitted to the study site in the afternoon of Day 7 and remain at the study site until discharge post-surgery. The surgery will take place in the morning of Day 8, 12 hours (window -1/+3 hrs) after last dose of study treatment.

The surgery may be delayed by up to 7 days, in which case the study treatment will continue to be applied twice daily up to 14 days. If the surgery is delayed by more than 7 days, the subject should be withdrawn from the study. Subject Withdrawal/Early Termination assessments will be conducted (See Section 6.4 Subject Withdrawal). No further PK blood samples will be collected and the rescheduled surgery will not be part of the study.

On Day 7 (pre-surgery), the following procedures will be completed and results recorded in source documents:

- Collect all returned study treatment
- Collect all returned rescue medication
- Review concomitant medications
- Review any AEs (continuing up to surgery)
- Collect a blood sample for pharmacokinetic analysis within 1 hour prior to last dosing.
- Dose subject with final dose of study treatment (12 hours (window -1/+3 hrs) prior to surgery)

**After dosing**, (ie. Between final dosing with study treatment and prior to surgery) the following procedures will be completed:

- Conduct physical examination and collect vital signs (BP, PR, RR, temperature)
- Collect standard 12-lead ECG measurements
- Following at least a 4 hour fast, collect blood and urine specimens for safety laboratory tests
- Collect one blood sample for diclofenac levels —at least 3 hours after dosing and more than 3 hours before surgery
- The subject will be prepared for surgery according to the procedures of the surgical center; if shaving of the knee area is required, this should occur as close as possible to the surgery but in any event no less than 3 hours after dosing

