### 1.1 Study Design

Approximately fifty (50) male and female OA subjects, who, at the time of screening, are  $\geq$ 50 years old, will be randomized in a 2:1 ratio: two thirds will receive DDEA 2.32% gel treatment and one third placebo gel.

After providing informed consent to participate in the study the subjects will need to forego any NSAID or cyclo-oxygenase 2 (COX-2) treatment for at least 7 days prior to starting study treatment (Visit 2) in order to allow wash-out of existing therapy and thus avoiding confounding the effect of the study treatments. Dosing will be scheduled to commence seven days prior (at minimum) to the scheduled surgery and will occur twice a day following dosing instructions. If surgery is delayed dosing with study treatment can continue up to 14 days.

A schematic of the study design is provided in Figure 1-1.

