### 1.4 Sample Size Calculation

A formal estimation of sample size was not carried out. The sample size selected (approximately 30 subjects on active, 15 subjects on placebo control) for the present study is in general agreement with similar studies (Benito 2005, Gallelli 2013, Gallelli 2012, Alvarez-Soria 2006, Fowler 1983, Efe 2014) and is deemed adequate to provide information on diclofenac concentration(s) in treated knee synovial tissue and synovial fluid.

Approximately 50 subjects will be randomized to account for 10% dropout and ensure evaluable data for 45 subjects who underwent the surgery.

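### The compliance percentage in SAP 4.3.1 counts planned applications only up to the last dose, so a subject who misses only whole final days scores 100%

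*SAP*

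**What the plan says.** SAP 4.3.1 (Study Drug Compliance) makes three statements that have to fit together.

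- The measure: "Percentage of scheduled applications made is defined as the number of applications made divided by the number of applications planned".
- The schedule: application starts on the day of randomization (Day 1), and the gel will "continue to be applied twice daily until and including the day before surgery".
- The planned number: two times "date of last application-date of first application +1".

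The percentage is summarized for the analysable population in Table 14.2.1.1, beside the total number of applications and the number of subjects with at least 12. Protocol 10.2.4.1 plans only the 12-application count. The percentage and its denominator are therefore new in the SAP, and SAP Table 5-1 does not list them as a change.

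No section of the SAP defines the date of last application as a scheduled date. The nearest related text is SAP 4.1.1, where the disposition listing contains "date of first and last dose, completion status (Yes/No), completion or termination date". There the last dose date is something recorded for each subject.

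**The concern.** The schedule ends at surgery, but the formula ends at the last application. If that is the last dose given, the denominator shrinks whenever a subject stops early. The percentage then depends on when doses were missed as well as on how many.

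The doses that drop out of sight are the ones closest to sampling. The endpoints are defined at 12 hours after the last application. A subject last treated on the evening of Day 6 and operated on in the morning of Day 8 is sampled roughly 36 hours after dosing (12 + 24), yet would be shown as fully compliant.

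Such a subject can be in the table. The analysable population takes subjects from the safety population "who completed the surgery and have evaluable synovial tissue or synovial fluid sample", with no requirement that the final dose was given.

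**Working it through.** **Inputs**

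- Two doses are possible on Day 1, because the baseline visit is in the morning (Protocol 6.2.1).
- Undelayed surgery is on the morning of Day 8 (Protocol 6.2.3).
- Surgery may be delayed by up to 7 days, so to Day 15 at the latest: "If the surgery is delayed by more than 7 days, the subject should be withdrawn from the study" (Protocol 6.2.3).
- Planned arm sizes: "approximately 30 subjects on active, 15 subjects on placebo control" (SAP 1.4).

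The documents state no planned count or compliance percentage to reproduce.

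**Formulas**, with first application on Day 1, last application on Day L and surgery on Day S

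- SAP formula: planned = 2 × (L − 1 + 1) = 2L.
- SAP schedule sentence (Day 1 through Day S − 1): planned = 2 × (S − 1). This is 14 for Day 8, 20 for Day 11 and 28 for Day 15.

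For a subject dosed twice on every day up to Day L, the number made is 2L. The SAP formula then gives 2L/2L = 100% whatever L is.

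**Results**

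| Surgery | Doses missed | Made | SAP formula | Schedule to day before surgery |
|---|---|---|---|---|
| Day 8 | none | 14 | 14/14 = 100% | 14/14 = 100% |
| Day 8 | Day 7 evening only | 13 | 13/14 = 92.9% | 13/14 = 92.9% |
| Day 8 | both on Day 4 | 12 | 12/14 = 85.7% | 12/14 = 85.7% |
| Day 8 | both on Day 7 | 12 | 12/12 = 100% | 12/14 = 85.7% |
| Day 8 | all on Days 6 and 7 | 10 | 10/10 = 100% | 10/14 = 71.4% |
| Day 11 | six mid-course, dosed on Day 10 | 14 | 14/20 = 70.0% | 14/20 = 70.0% |
| Day 11 | all after Day 7 | 14 | 14/14 = 100% | 14/20 = 70.0% |
| Day 15 | all after Day 7 | 14 | 14/14 = 100% | 14/28 = 50.0% |

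The two denominators differ only when whole final days are missed.

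**Effect on an arm mean, per affected subject**

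- Day 8 case, both Day 7 doses missed: the error is 100 − 85.7 = 14.3 points. That is 14.3/30 = 0.48 points in the active arm or 14.3/15 = 0.95 in the placebo arm.
- Day 11 case, stopped after Day 7: the error is 100 − 70.0 = 30.0 points. That is 30/30 = 1.0 or 30/15 = 2.0 points.

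**Does the 12-application count catch these subjects?** Only in part. With Day 8 surgery it flags a subject who misses two or more final days (10 or fewer applications). It does not flag one who misses only Day 7, who has exactly 12. With Day 15 surgery, 14 of 28 also passes.

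**The case against.** The strongest reply is that this is an undefined term and not an error. The schedule sentence stands directly before the formula, so the date of last application could be read as the scheduled last day. The formula then gives the right 14. That reading is possible, but the SAP does not state it. A programmer would naturally use the recorded last-dose date, so the text needs changing under either reading.

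The second reply concerns delayed surgery. SAP 1.1 says "If surgery is delayed dosing with study treatment can continue up to 14 days", which can be read as permissive. On that reading, doses after Day 7 might not count as scheduled, and 14/14 would be defensible for the Day 11 subject. The 30.0-point figure does rest on the schedule sentence in SAP 4.3.1 and the similar wording in Protocol 6.2.3, both of which have dosing continue until surgery. The passages need reconciling. The Day 8 result does not depend on this.

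The remaining points are about reach, and they stand:

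- Every dose is applied by a nurse (Protocol 5.3) and the last is given on site, so a wholly missed final day should be rare.
- Such a case would show in the total number of applications and in Listings 16.2.1.1 and 16.2.5.2. It should also appear among the protocol deviations, because the interval from last dose to surgery would fall outside its window. None of these corrects the percentage.
- Primary and secondary summaries carry no compliance condition, and the per-protocol population has no analyses assigned to it.
- Poor compliance can exclude a subject from the PP-PD population, which is analysed, but no text ties that decision to this percentage.

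**Conclusion.** The concern holds. As written, the planned count does not follow the schedule that the same section sets out, and a subject who misses only whole final days is reported as 100% compliant. For Day 8 surgery with Day 7 missed, the overstatement is 14.3 points for the subject and 0.48 or 0.95 points for the arm mean. For Day 11 surgery with dosing stopped after Day 7, it is 30.0 points for the subject and 1.0 or 2.0 for the arm mean, provided the days of delay count as scheduled.

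This assumes that the date of last application means the last dose given, that dosing starts with the morning dose on Day 1, and that the arms reach their planned sizes. The documents do not give the number of delayed surgeries or missed final days, so the total effect cannot be stated. It is confined to a descriptive row in Table 14.2.1.1. The correction should be made because the reported figure would be wrong and the change is small.

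**What to change.** In SAP 4.3.1, define the planned number of applications as 2 × (date of surgery − date of first application). This gives 14 for Day 8 surgery and 28 for Day 15, and equals the present formula when dosing is complete. If the scheduled end date was intended all along, replacing the date of last application with the day before surgery gives the same numbers.

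State in the same place which days count as scheduled when surgery is delayed, and reconcile SAP 1.1, SAP 4.3.1 and Protocol 6.2.3 on that point. Leave the protocol's count of subjects with at least 12 applications unchanged.

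The cost is one changed derivation in one table, with no new data. The surgery date can be taken from the intraoperative plasma sample, whose collection time goes in the CRF (Protocol 7.2.1). If that sample is missing, the collection times noted for synovial tissue and fluid can serve (Protocol 7.2.2). Reported compliance may come out slightly lower.

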### 4.3.2 Study Drug Exposure

Study drug exposure will be summarized descriptively by treatment group for the Safety population, including the following summaries: total number of applications and total weight of gel used (Table 14.3.1).

### 4.3.3 Prior and Concomitant Medication

Any medications taken by subject within 90 days before the screening visit (Visit 1) and up to the last study visit (Visit 4) during the study will be recorded in the case report form (CRF).

All medications will be coded using the GSK Drug coding dictionary (GSKDRUG), which will be updated whenever available throughout the life of the study.

For purposes of analysis, prior medications are defined as any medications with a stop date that is prior to the initial study drug dosing date (Day 1) and concomitant medications are defined as any medications with a start date on or after the initial study drug dosing date (Day 1) or any medications with a start date prior to the initial study drug dosing date and a stop date after the initial study dosing date.

> GlaxoSmithKline Consumer Healthcare Confidential Page 13 of 22

For medications with partial start or stop dates, the partial dates will be imputed according to Table 4-1 and then will be categorized as prior medication or concomitant medication according to the definitions. Medications with completely missing dates will be included in the concomitant medication summary.

Imputation rules for the start or stop date of missing or incomplete medications are presented in Table 4-1.

	Missing	Imputation	Exception
Start date (concomitant medication)	Day	01	Default to Study Day 1 if an event starts the same year and month as Day 1 and the stop date contains a full date and the stop date is later than Day 1; Otherwise If the stop date is prior to Day 1, default to 1 day prior to the stop date
	Day/Month	01Jan	Default to Study Day 1 if an event started the same year as Day1 and the stop date contains a full date and the stop date is later than Day 1; Otherwise If the stop date is prior to Day 1, default to 1 day prior to the stop date
	Day/Month/Year	No imputation	Assume start prior to study entry.
Stop date (concomitant medication)	Day	Last day of the month	Default to the End of Study Date if the concomitant medication stopped the same year and month as the End of Study Date.
	Day/Month	31DEC	Default to the End of Study Date if the concomitant medication stopped the same year as the End of Study Date.
	Day/Month/Year	No imputation	Assume stops after study

## Table 4-1Imputation rules for the start or stop date of missing or incomplete
medications

Tables and listings described in this section will be presented for the safety population. The prior and concomitant medications listing will include the preferred term, indication, a flag indication of prior or concomitant, single dose, frequency, unit, route, start date, and end date or ongoing at final visit (Listing 16.2.5.7). The significant non-drug therapies listing will

GlaxoSmithKline Consumer Healthcare Confidential Page 15 of 22 include the name of non-drug therapy, a flag indication of prior or concomitant, start date, and end date or ongoing at final visit (Listing 16.2.5.8).

Concomitant medications will be reported by GSK-Drug Anatomical Therapeutic Chemical (ATC) classification level 1 (Body System) and ingredient (Table 14.3.2). Drugs that are composed of a combination of ingredients will be displayed according to the ATC classifications of the ingredients, not of the combination.

### 4.3.4 Rescue Medication

Rescue medications used during the study treatment period (number of subjects that used paracetamol, number of days on paracetamol, percentage of days on paracetamol and total dose of paracetamol taken) will be presented by treatment group for the analysable population (Table 14.2.1.2). This summary will only include those subjects who used rescue medications during the study treatment period.

By-subject listing of all rescue medications, used before start of the study treatment and during the study treatment, will be produced for the safety population (Listing 16.2.5.3).

### 4.4 Analysis of Primary Objective

The primary objective of this study is to determine whether diclofenac penetrates into the treated knee joint following repeated topical administration of diclofenac diethylamine 2.32% gel.

### 4.4.1 Primary Endpoints

### 4.4.1.1 Primary Endpoints Definition

The primary endpoints are diclofenac concentrations in treated knee synovial tissue and synovial fluid after 7 days topical application of study treatment to the knee (12 hours after last application).

### 4.4.1.2 Statistical Hypothesis, Model, and Method of Analysis

The success criterion of this study is that diclofenac can be detected within the treated knee synovial tissue or synovial fluid after 7 days treatment.

Synovial tissue and synovial fluid diclofenac concentrations will be summarized descriptively by treatment group in both the arithmetic and the logarithmic scale (Table 14.2.2.1 and Table 14.2.3.1). The tables will present the proportion of subjects with values above the limit of quantification (LOQ) with its two-sided 95% confidence interval estimated by Wilson score interval. The mean, SD, min, P10, Q1, median, Q3, P90, max will be calculated after replacing values below the LOQ by LOQ/2 for treatment group and by 0 for placebo group. The geometric mean will also be calculated for treatment group with a two-sided 95% confidence interval assuming data on the logarithmic scale are normally distributed. Boxplots for study treatment group will be produced on the original data (Figure 14.2.1 and Figure 14.2.3). There is no formal hypothesis testing to be performed.

GlaxoSmithKline Consumer Healthcare Confidential Page 16 of 22 The analyses will be performed on the analysable population.

